10.4 Stopping Rules

Considering the low-risk of this study, no interim analyses are proposed and stopping rules have not been established. However, the study may be discontinued at any time by the IRB, the NIMH, the OHRP, or other government agencies as part of their duties to ensure that research participants are protected.

11 Data Handling and Record Keeping

11.1 Confidentiality

Confidentiality of study data will be maintained by numerically coding all data, by disguising identifying information, and by keeping all data in password-protected, encrypted computer files. All information obtained from participants will be accessible only to research staff. Study staff will maintain participant privacy by securing records using password-protected, encrypted databases. In meetings when study procedures are reviewed and issues of compliance are raised, participants will not be identified by name unless necessary, and if necessary only by first name. Project meetings will be held in private conference rooms.

Data will be obtained from electronic assessments completed by study participants and usage data from the study website. Personally identifiable information (PII), assessment responses, and usage data will be kept in separate datasets. They will be linked only with a randomly generated ID variable that is included in all data. Although the datasets will be housed on the same server (e.g., REDCap for assessment and self-report data, the intervention website for usage data and content review data), they will otherwise be completely separate. The PII dataset will be deleted upon completion of data collection and cleaning. AE reports and annual summaries will not include subject-identifiable material. Multiple levels of password protection will be utilized and access will be denied to non-study personnel. No identifiable information will be stored on laptops or transportable devices in this study. Further, REDCap and website servers will be physically stored in high security areas and study desktops will be located within a secured building.

If it is discovered that despite security precautions electronic data has been hacked, or if someone has illegally gained access to any data, the PI will determine to what extent the hacking has been successful. The PI will promptly inform the appropriate authorities to the extent of the hacking (e.g., BU, the IRB, NIH project officer, and, if appropriate, the police department). The PI in collaboration with the above authorities will determine what action, if any, is appropriate. In the unlikely event that hacking occurs, an attempt will be made to contact every participant potentially affected by the hacking to inform them that their data may have been accessed. Legal recourse will also be sought to

prevent further use or distribution of the data if we are able to identify the individual or agency who hacked the data. Upon reasonable suspicion that the data has been hacked, all data collection will be suspended until the incident has been reviewed and a secure means of continuing to obtain and store data has been re-established.

Because of the sensitive nature of the data we are collecting, we have received a Certificate of Confidentiality for this study to ensure that participants’ data cannot be subpoenaed with a court order.

The study monitor or other authorized representatives of the sponsor may inspect all documents and records required to be maintained by the investigator. The study will permit access to such records.

11.2 Source Documents

There are two sources of data: (a) participant self-report and (b) usage data:

- **Self-report data:** will be collected via content ratings for each piece of intervention content and the assessments. Assessments for the pilot RCT will be conducted at baseline, post-intervention (3 week after baseline), and follow-up (15 weeks after baseline). Assessment data will be collected using a secure online survey software system, namely, REDCap.⁶⁰ Content ratings will be collected through the intervention website.
- **Usage data:** will include banner ad click-through rate, time spent on intervention content, and number of intervention website log-ins. Banner ad click-through rate will be acquired from the advertising websites. Time spent on each piece of intervention content and number of intervention website log-ins will be collected via the intervention website.

Only authorized study personnel will have access to the data.

Self-report measures. An overview of the constructs and assessed behaviors is provided in Table 3.

Descriptive measures and moderators.

Socio-demographics. Age, race/ethnicity, birth sex, gender identity, sexual orientation, education level, living situation, and zip code will be asked using standard formats. **Legal Guardians.** Participants will be asked questions about their legal guardians and how “out” they are about their sexual attraction to male partners.¹⁵ **Outness.** Participants will also be asked about their overall degree of “outness.”^{37,87} **Healthcare access/use.** Access and use of healthcare services, including HIV/STI testing.⁷⁷ **Substance use.** The impact of participants’ use of alcohol and other drugs will be assessed using the CAGE Adapted to Include Drugs (CAGE-AID).⁸⁸ Participants will also be asked about which drugs they used recreationally in their lifetime. **Mental Health**

Table 3. Measures: Purpose and Timing of Administration

Purpose	Construct or Behavior	Baseline	Intervention	Post Intervention	Follow-up
Descriptors / Moderators	Socio-demographics	x			
	Legal Guardians	x			
	Outness	x			x
	Healthcare access/use	x			x
	Substance Use	x			x
	Mental Health	x			x
	Sexual Abuse History	x			x
	Sexual Education Exposure	x			x
Feasibility	Study recruitment	x			
	Study retention			x	x
	Intervention metrics		x	x	
Acceptability	Webpage ratings		x		
	Satisfaction survey			x	
Exposure	SEOM exposure	x			x
Mediators	Identification with SEOM actors	x		x	x
	Perceived norms of SEOM behavior	x		x	x
	Expectancies about SEOM behavior	x		x	x
	Perceived consequences of SEOM behavior	x		x	x
Preliminary Efficacy	Sexual risk behaviors	x			x
	Antecedents to sexual risk	x		x	x
	Media literacy	x		x	x
	Sexual health knowledge	x		x	x

will be assessed using the PHQ-4. *Sexual abuse history* will be assessed using the sexual abuse subscale of the Childhood Trauma Questionnaire (CTQ). *Sexual education exposure*. Sources of sexual education (e.g., parents, school, online) and coverage male-male sexual health-related topics will be assessed.¹⁵

Feasibility measures. To assess study feasibility, banner ad click-through rate, number of individuals recruited per week, and the percentage of individuals who were eligible; assented; dropped out and lost to follow-up will be calculated. To assess the feasibility of the media literacy intervention we will calculate intervention metrics (i.e., time spent on each piece of intervention content, percentage who complete all intervention content).

Acceptability measures. To assess acceptability, media literacy intervention participants will be asked to complete content ratings on each piece of intervention content using a 5-star rating system and an open text field. Participants will also be given the option of providing written feedback on each piece of content as well. All participants will also be asked to complete a satisfaction survey at the post-intervention follow-up.⁴⁸ Participants will be asked to report on study procedure acceptability (e.g., acceptability of recruitment, consent, assessment procedures). Intervention participants will be asked to report how informative, interesting, and helpful the intervention was; how likely they would be to recommend it to friends; and if they have suggestions for how it could be improved. Participants in the control group will be asked which website they went to, if any, and to report how informative, interesting, and helpful the website was; as well as how likely they would be to recommend it to friends. The satisfaction survey will include a combination of Likert scale and open-ended responses.

Exposure measure and mediators. Sexually explicit online media (SEOM) use will be established through a measure developed in a previous study of SEOM use among adult MSM³⁷ and adapted for use with ASMM.²⁶ This measure covers topics including: frequency and timing of usage; prevalence of viewing portrayed behaviors in SEOM; preferences for condoms use in SEOM; arousal during use; identification with SEOM actors; perceived norms of SEOM behaviors; expectancies about portrayed behaviors; perceived consequences of portrayed behaviors; and beliefs about the influence of SEOM on behaviors within the participant and on other MSM (i.e., perceived norms).

Preliminary Efficacy measures. To conduct exploratory assessments of intervention efficacy, we will measure three primary outcomes: sexual risk, media literacy, and sexual health knowledge. *Sexual risk.* Sexual risk behaviors and antecedents to sexual risk behaviors will be assessed. Participants will be asked aggregate information about the number of sex partners, gender of partners, HIV-status of partners, romantic/primary partner status, sexual activities and condom use, and substance use with sex in the prior 3 months. Participants will be asked to report only on voluntary sexual behavior (i.e., not forced). To optimize the accuracy of these reports, counts of behaviors will be asked in an open response format.⁴⁹⁻⁵² Antecedents to sexual risk-taking include intentions to have sex and for sexual communication (e.g., communication about HIV/STI status, condom use)^{44,53} as well as condom attitudes.⁵⁴ *Media literacy skills* will be assessed using questions adapted from the two previous sexual health media literacy interventions, including awareness of SEOM myths, awareness of SEOM influence, and SEOM skepticism.⁴²⁻⁴⁴ *Sexual health knowledge* will be determined by assessing HIV⁵⁵ and STI⁵⁶ transmission knowledge; HIV/STI prevention method knowledge;⁵⁷ and the levels of HIV/STI transmission risk (low, medium, high) associated with sexual behaviors (e.g., oral sex, anal sex).⁵³

11.3 Case Report Forms

N/A

11.4 Study Records Retention

All study records will be retained in electronic form for at least seven years after completion of the study.

12 Statistical Plan

12.1 Study Hypotheses

We hypothesize that the YM&M intervention will be feasible and acceptable. We further hypothesize that sexual risk behaviors will decrease and media literacy skills and sexual health knowledge will increase by greater amounts in the intervention group compared to the control group at post-intervention and 3-month follow-up.

12.2 Sample Size Determination

Sexual health media literacy interventions have an overall effect size of 0.21 - 0.38 on antecedents to sexual risk behaviors.⁴²⁻⁴⁴ For this exploratory study, we conservatively anticipate a Cohen's $d = 0.20$ between 2 groups. With the current sample size ($N = 150$) and a two-sided $\alpha = 0.05$, we have 52% power to determine an effect size 0.20. With a two-sided $\alpha = 0.05$ and 80% power ($\beta = 0.20$) we would require retention of a total sample size of 192. Considering the scope of the award, recruitment and retention of this sample size is not feasible. The proposed sample size is adequate to evaluate feasibility and acceptability of the intervention and gauge whether the intervention effects are encouraging.

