4.2.2 Secondary Outcome Measures

The **secondary outcomes** will measure preliminary efficacy (i.e., changes in sexual risk behaviors, media literacy skills, and sexual health knowledge).

Sexual risk. Sexual risk behaviors and antecedents to sexual risk behaviors will be assessed. Participants will be asked about the number of sex partners, gender of partners, HIV-status of partners, romantic/primary partner status, sexual activities and condom use, and substance use with sex in the prior 3 months. Participants will be asked to report only on voluntary sexual behavior (i.e., not forced). To optimize the accuracy of these reports, counts of behaviors will be asked in an open response format.^{49–52} Antecedents to sexual risk-taking include intentions to have sex and for sexual communication (e.g., communication about HIV/STI status, condom use)^{44,53} as well as condom attitudes.⁵⁴

Media literacy skills will be assessed using questions adapted from the two previous sexual health media literacy interventions, including awareness of SEOM myths, awareness of SEOM influence, and SEOM skepticism.^{42–44}

Sexual health knowledge will be determined by assessing HIV⁵⁵ and STI⁵⁶ transmission knowledge; HIV/STI prevention method knowledge;⁵⁷ and the levels of HIV/STI transmission risk (low, medium, high) associated with sexual behaviors (e.g., oral sex, anal sex).⁵³

5 Study Design

The study design is a pilot randomized controlled trial (RCT) with two conditions (i.e., YM&M intervention vs. control) and three online assessments (i.e., baseline, post-intervention, 3 month follow-up). Prior to randomization all participants ($N = 150$) will complete a baseline assessment. Participants will then be randomly assigned (1:1 randomization) to the intervention or to the control group. The randomization schedule will be generated using a permuted block randomization procedure with small, random-sized blocks. Following receipt of the intervention or control, participants will be asked to complete a post-intervention assessment and a 3-month follow-up. Data will include self-report and usage data. See Appendix 1 for a schematic of the study design and participant flow and Appendix 2 for a schedule of events.

6 Potential Risks and Benefits

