12.3 Statistical Methods

Because this is a small pilot study, analyses are not powered to detect intervention effects or formally test mediation or moderation. To determine feasibility of conducting a RCT, we will calculate the percentage of individuals who were: eligible; assented; were randomized; and completed the post-intervention and 3-month follow-up. To determine feasibility of the intervention, we will calculate the total time spent on each intervention page as well as the percentage of individuals who complete the intervention. To determine acceptability of the intervention, we will calculate mean content ratings for the intervention pages and satisfaction surveys as well as inspect open-ended responses. As a secondary goal and to obtain preliminary evidence of efficacy of the online media literacy intervention, we will examine the within- and between-group differences at each follow-up for all three efficacy measures (i.e., sexual risk, media literacy, sexual health knowledge) using a series of longitudinal mixed effects models, controlling for baseline values, as well as any group differences.

13 Ethics/Protection of Human Subjects

This study is to be conducted according to applicable US federal regulations and institutional policies (which are based in federal regulations, guidance, and ICH Good Clinical Practice guidelines).

This protocol and any amendments will be submitted to the Boston Medical Center and Boston University Medical Campus IRB, for formal approval of the study conduct. The decision of the IRB concerning the conduct of the study will be made in writing to the investigator. A copy of the initial IRB approval letter will be provided to NIMH before commencement of this study.

All subjects for this study will be provided assent material describing this study and providing sufficient information for subjects to make an informed decision about their participation in this study. The assent material will be submitted with the protocol for review and approval by the IRB. The assent of a subject, using the IRB-approved assent material, must be obtained before that subject is submitted to any study procedure. Assent will be documented as required by the IRB.

14 Literature References

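### The stated 52% power at N = 150 and the required size of 192 do not follow from d = 0.20 between two groups, and they contradict each other: the stated inputs give about 23% and 788

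*Combined protocol and SAP*

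**What the plan says.** Section 12.2 cites effects of 0.21 to 0.38 from earlier media literacy interventions on antecedents of sexual risk. It then adopts Cohen's d = 0.20 between the two groups as a conservative value, with two-sided alpha 0.05. Two results follow:

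- At N = 150, "we have 52% power to determine an effect size 0.20".
- For 80% power, "we would require retention of a total sample size of 192", which the section calls infeasible within the award.

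It concludes that 150 is enough to assess feasibility and acceptability and to judge whether effects look encouraging. No baseline correlation, repeated-measures gain or attrition rate is given.

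Section 5 has participants "randomly assigned (1:1 randomization) to the intervention or to the control group", so 75 per arm. Section 12.3 says the pilot is not powered for intervention effects. It plans to examine efficacy at each follow-up "using a series of longitudinal mixed effects models, controlling for baseline values".

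**The concern.** Every input for a standard two-group calculation is stated, and a difference of 0.20 SD is small. Power above one half with 75 per arm, or 80% power with 96 per arm, is not plausible for an effect of that size. The step from 52% at 150 to 80% at 192 is also too steep for a 28% increase in sample size.

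These are the only power and required-size figures in the document. As printed, they say the pilot has roughly an even chance of detecting the planned effect and that a powered trial is 42 participants away (192 − 150). A reader could give too much weight to a null efficacy result, or carry 192 forward as the size of the next trial.

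**Working it through.** **Inputs.** d = 0.20 between groups, two-sided alpha 0.05, N = 150, target power 80% (section 12.2). Allocation 1:1, so n = 75 per arm (section 5). All participants are taken as analysed, since no attrition rate is given.

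**Power at N = 150.** The noncentrality is δ = d·√(n/2) = 0.20·√37.5 = 1.225. Power ≈ Φ(1.225 − 1.960) = Φ(−0.735) = 23.1%. The noncentral t gives 22.9%. The plan's 52% is not reproduced.

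**N for 80% power.** n per arm = 2(1.960 + 0.842)²/0.20² = 392.4, so 393 per arm or 786 in total. With the noncentral t, 393 per arm gives 79.96%, so 394 per arm or 788 are needed. The plan's 192 is not reproduced; 788/192 = 4.1.

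**Power at N = 192.** δ = 0.20·√48 = 1.386, which gives 28%.

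**Do the two figures agree with each other?** For a fixed model, δ grows with √N. Power of 52% needs δ = 1.960 + 0.050 = 2.010, and 80% needs δ = 2.802.

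- If 52% at 150 is right, 80% needs 150·(2.802/2.010)² ≈ 291 (290 with the t), and power at 192 is 62%.
- If 80% at 192 is right, then at 150 δ = 2.802·√(150/192) = 2.476 and power is 70%.

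**Effects the figures would fit.** In a two-sample t test, 52% at 150 needs d = 0.33 and 80% at 192 needs d = 0.41. The second lies above the top of the cited range. At d = 0.38, N for 80% power is still 218.

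**Other readings tried.**

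| Reading | Power at 150 | N for 80% |
|---|---|---|
| One-sided alpha 0.05 | 34% | 620 |
| One-sample or paired, d = 0.20 | 68% | 199 |
| Cohen's f = 0.20, two groups | 68% | above 192 (79% at 192) |
| Correlation of 0.20 | 69% | 194 |

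Reading 150 as a per-arm size gives 41% two-sided and 53% one-sided. None of these yields both printed figures.

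**Baseline adjustment (assumed correlation r).** With one follow-up, the residual variance is 1 − r². For r = 0.5 to 0.7, power at 150 is 29% to 40%, and N for 80% is 590 to 402. If both follow-ups are averaged, with r common to all three occasions, the variance is (1 + r)/2 − r². Power is then 41% to 53% and N is 394 to 284.

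The variance needed is (0.20/0.330)² = 0.367 for 52% at 150 and (0.20/0.406)² = 0.243 for 80% at 192. With one follow-up that means r of about 0.80 and 0.87. With the average it means about 0.69 and 0.82. Neither model gives both figures at one value of r.

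**Precision.** Unadjusted, the 95% half-width for the standardized difference at N = 150 is 1.96·√(2/75) = 0.32. The difference detectable with 80% power is 0.46. With an assumed 80% retention (60 per arm), power is 19% and the half-width is 1.96·√(2/60) = 0.36.

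**The case against.** The strongest reply is that 23% and 788 describe an unadjusted comparison at one time point, whereas section 12.3 plans baseline-adjusted longitudinal models. If both follow-ups are averaged and r is about 0.69, power at 150 is about 52% and the required size about 292, so 192 could be a one-digit slip. The two figures would also agree if the 52% had been computed on about 99 retained participants: 192·(2.010/2.802)² ≈ 99, a loss of about 34%.

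It stands that 23% and 788 must be labelled unadjusted and that the planned analysis may do better. The rest is conjecture. No correlation or attrition rate is stated, and 12.2 ties the 52% to the full 150. Section 12.3 compares groups at each follow-up, not on their average. Table 1 shows sexual risk behaviors measured only at baseline and at the final follow-up, so averaging is not possible for that outcome. If 292 was meant, the printed 192 is still wrong. The attrition route still needs d of about 0.41 in an unadjusted comparison.

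A second reply is that this is a pilot which admits low power, with feasibility and acceptability as primary outcomes, and that no decision rule uses 52% or 192. That is fair and limits the harm. It does not make the figures correct.

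**Conclusion.** The concern holds. For the inputs in 12.2, in an unadjusted two-group comparison with everyone analysed, power at 150 is 23% rather than 52%, and 80% power needs 788 rather than 192. That is 638 more than planned (788 − 150), not 42. Independently of d, the two printed figures cannot come from one model if both count analysed participants.

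The adjusted results depend on assumed correlations and do not rescue the pair. Feasibility and acceptability are unaffected. What changes is the efficacy reading: with an unadjusted interval of about ±0.32, an observed difference of 0.20 would be compatible with no effect or with modest harm.

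**What to change.** Reword section 12.2 in one of two ways.

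1. If a baseline-adjusted or repeated-measures calculation was intended, state the model, the assumed correlation, the number of follow-ups used and the retention. Then report one power and one required N from that same model.
2. Otherwise, replace the figures with text such as:

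> With 75 per group and two-sided alpha 0.05, an unadjusted comparison has about 23% power for d = 0.20. Power of 80% would need about 788 participants (394 per group). The difference detectable with 80% power is d of about 0.46. The 95% confidence interval for the standardized difference will be about ±0.32, and wider after attrition.

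Either way, the sentence on judging whether effects are encouraging should rest on that precision. The cost is wording in one section and, under the second option, a less favourable power statement. N = 150, the design and the primary outcomes do not change.

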12.3 Statistical Methods

Because this is a small pilot study, analyses are not powered to detect intervention effects or formally test mediation or moderation. To determine feasibility of conducting a RCT, we will calculate the percentage of individuals who were: eligible; assented; were randomized; and completed the post-intervention and 3-month follow-up. To determine feasibility of the intervention, we will calculate the total time spent on each intervention page as well as the percentage of individuals who complete the intervention. To determine acceptability of the intervention, we will calculate mean content ratings for the intervention pages and satisfaction surveys as well as inspect open-ended responses. As a secondary goal and to obtain preliminary evidence of efficacy of the online media literacy intervention, we will examine the within- and between-group differences at each follow-up for all three efficacy measures (i.e., sexual risk, media literacy, sexual health knowledge) using a series of longitudinal mixed effects models, controlling for baseline values, as well as any group differences.

13 Ethics/Protection of Human Subjects

This study is to be conducted according to applicable US federal regulations and institutional policies (which are based in federal regulations, guidance, and ICH Good Clinical Practice guidelines).

This protocol and any amendments will be submitted to the Boston Medical Center and Boston University Medical Campus IRB, for formal approval of the study conduct. The decision of the IRB concerning the conduct of the study will be made in writing to the investigator. A copy of the initial IRB approval letter will be provided to NIMH before commencement of this study.

All subjects for this study will be provided assent material describing this study and providing sufficient information for subjects to make an informed decision about their participation in this study. The assent material will be submitted with the protocol for review and approval by the IRB. The assent of a subject, using the IRB-approved assent material, must be obtained before that subject is submitted to any study procedure. Assent will be documented as required by the IRB.

14 Literature References

